4. **Importance of preeclampsia in the U.S.** Preeclampsia, a potentially fatal pregnancy condition characterized by high blood pressure, is estimated to complicate 3 percent to 6 percent of all pregnancies¹⁻². The rate of preeclampsia in the U.S. has increased 25 percent in the past two decades²². Preeclampsia is a leading cause of maternal and infant illness and death^{1;4-5;8}. Non-Hispanic Black women carry a 3- to 4 fold greater risk of dying from pregnancy-related preeclampsia^{3;12;20}. For example, preeclampsia is associated with 20-30% preterm births and 15% low birth weight^{1;5}. Moreover, a significant number of women who get preeclampsia are at increased risk for cardiovascular disease after pregnancy and throughout their lives.^{1;8;23}

C. Rationale

1. We posit that the implementation of HGPC-T for continuous high blood pressure monitoring is a critical step in closing disparities in preeclampsia. This research has the potential to reduce preeclampsia disparities by considering system change in the delivery of maternal care, continuous monitoring of blood pressure, reducing barriers in transportation and time off from work, improving patient hypertension education, and improving social support and peer-to-peer learning.
2. This research has the potential to reduce preeclampsia disparities by considering system change in the delivery of maternal care continuous monitoring of blood pressure, reducing barriers in transportation and time off from work, improving patient hypertension education, and improving social support and peer-to-peer learning.

3. The study may reduce preeclampsia and improve management of pregnancy-related hypertension.

II. Research Plan and Design

- A. Study Objectives:** The objective is to enhance the Centering GPC intervention with telehealth and take care of your blood pressure (TCYB) intervention for hypertension monitoring.
- B. Study Type and Design:** We will use REDCap software to assign 72 women in a 2:1 randomization scheme in variable block sizes to, respectively, Centering -Health, Empowerment, Reproduction (HER) or usual doula care. You will have a 2 out of 3 chance to participate in the intervention. "Group assignments are random, like flipping a coin or rolling the dice."
- i. Group 1-Non-Intervention
 1. Receive usual doula prenatal care including regular prenatal care visits.
 2. Participants will complete a baseline survey, antepartum study survey, and for postpartum survey

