 - ii. Group 2- Centering HER intervention
 1. Once selected for the study, you will participate in usual prenatal care visits with an OBGYN, 7 doula led virtual intervention sessions visits with an OBGYN fellow oversight.
 2. The 7 virtual meeting will be an hour and a half and led by a doula. A research staff member will be present to help with the coordination of the virtual intervention.
 3. You will receive 7 virtual visits with a group of women participating in the study
 4. Each telehealth/virtual visit will discuss blood pressure/hypertension, blood pressure, nutrition, weight management, exercise, and risk factors for hypertension.
 5. Participants will receive a Bluetooth blood pressure cuff, apple watch (if applicable), and doula tailored care to take your blood pressure and weight at home.
 6. Self-report blood pressure and weight
 7. Participants will complete a baseline survey, antepartum study survey, and for postpartum survey.
 8. Keep a medication log if applicable

Intervention Table

Feature	Group 1: Non-Intervention (Usual Doula Care)	Group 2: Centering HER Intervention
Prenatal Care	Standard doula support + routine prenatal care with OB/GYN	Routine prenatal care + 7 virtual doula-led intervention sessions with OB/GYN fellow oversight

Feature	Group 1: Non-Intervention (Usual Doula Care)	Group 2: Centering HER Intervention
Doula Involvement	Yes – access to traditional doula support during prenatal visits	Yes – virtual group doula-led health education and coaching
Group Sessions	None	7 virtual group sessions (90 min each) with other pregnant participants
Session Topics	Not applicable	Hypertension, blood pressure, nutrition, exercise, risk factors
Technology Provided	None	Bluetooth BP cuff, Apple Watch (if applicable)
Self-Monitoring	No	Participants self-monitor and report blood pressure and weight
Survey Completion	Baseline, antepartum, and postpartum surveys	Baseline, antepartum, and postpartum surveys
Medication Tracking	No	Keep medication log (if applicable)
Research Staff Involvement	Minimal such as surveys, reported blood pressure	Yes – staff assist with coordinating virtual sessions

Timeline

Month	Activities	Milestones / Notes
Month 0-December	Study Launch + IRB Finalization– Finalize recruitment materials– Train staff + doulas– Set up data tracking and virtual platforms	IRB approval confirmed; staff orientation completed

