Month 1-February	Recruitment Begins– Begin enrolling both groups (target ~5 per group)– Distribute flyers, contact clinics, etc.	First 10 participants enrolled (5 intervention, 5 control)
Month 2-3	Continue Recruitment + Begin Intervention– Enroll next 10 participants– Begin Group 1 surveys– Intervention Group 1 starts Session 1	~50% enrollment milestone reached
Month 4	Recruit Final Cohort– Enroll remaining 36 participants– Distribute Apple Watches and BP cuffs– Start Sessions 1–2 for final intervention groups	72 participants fully enrolled (36 per group)
Month 5	Midpoint Engagement– Intervention: Sessions 3–4 (Blood Pressure, Nutrition)– Track self-monitoring data– Group 1 completes mid-surveys	Monitor adherence and troubleshoot any tech issues
Month 6	Continue Sessions + Surveys– Sessions 5–6: Physical activity, medication awareness– Group 2 logs vitals– Group 1 continues routine care + surveys	Most intervention participants complete 75% of sessions
Month 7	Final Session + Postpartum Planning– Session 7: Doula support, preparing for delivery– Collect	Sessions concluded for intervention group

Month	Activities	Milestones / Notes
	antepartum surveys– Encourage postpartum follow-up prep	
Month 8	Final Data Collection + Postpartum Surveys– Collect postpartum survey from both groups– Finalize weight/BP logs– Export and clean dataset	Study concludes; prepare for analysis and reporting

C. Sample size, statistical methods, and power calculation

1. Data will be checked for errors, inconsistencies, and missing values. Descriptive statistics (e.g., mean and standard deviation for continuous variables and number and percent for categorical variables) will be presented for all demographic variables, predictors of interest, and outcomes. Chi-square and 2-sample t-tests will be used to compare the outcomes among demographic groups and between different treatments.
2. The participants will receive education on nutrition and exercise, will be asked to monitor their blood pressure daily using blood pressure cuffs, and will receive the standard of care of 81mg of aspirin per day (if applicable).
3. This is a pilot project, so there is no power calculation for the project. The total number of participants is 72.

D. Subject Criteria (See Vulnerable Populations appendix, if applicable):

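### Arm 2 is delivered in shared doula-led groups, but the planned t-tests and chi-square tests treat all 72 women as independent; if outcomes correlate within groups, the standard error is too small

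*Protocol*

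**What the plan says.** **Allocation.** Protocol II.B uses REDCap to "assign 72 women in a 2:1 randomization scheme in variable block sizes". The unit of randomisation is the individual woman.

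**Delivery of Arm 2.** The Group 2 description in II.B says "You will receive 7 virtual visits with a group of women participating in the study" and "The 7 virtual meeting will be an hour and a half and led by a doula". The Intervention Table lists "7 virtual group sessions (90 min each) with other pregnant participants" for Group 2 and no group sessions for Group 1. The Timeline's Month 4 row speaks of starting sessions "for final intervention groups", so there is more than one group. Neither the number of groups nor their size is given.

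**Mechanism.** The Rationale (I.C) counts "improving social support and peer-to-peer learning" among the ways in which the intervention is expected to work.

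**Analysis.** II.C.1 states "Chi-square and 2-sample t-tests will be used to compare the outcomes among demographic groups and between different treatments", and V.A repeats it. Neither section mentions session group, doula, an ICC or a clustering adjustment. II.C.3 declares a pilot without a power calculation, although Aims 2 and 3 ask whether the intervention reduces preeclampsia.

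**The concern.** This is a partially nested design: individual randomisation, with shared delivery in one arm only. Women in one session group share a leader, peers and a calendar period, and the Protocol expects them to learn from one another. Their outcomes may therefore be more alike than those of women in different groups. The two-sample t-test and the chi-square test compute the Arm 2 variance as if every woman contributed independent information.

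With a positive ICC, the variance of the Arm 2 mean or proportion is understated. Confidence intervals for the between-arm difference are then too narrow and p-values too small. The same applies to comparisons among demographic groups that include Arm 2 women, although that case is not quantified here.

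A practical matter is also at stake. The instrument inventory in Appendix E lists no session-group or doula identifier. Without one, neither the adjusted interval nor the ICC that a later trial would need can be obtained.

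**Working it through.** The Protocol gives no figure to reproduce, so the check runs over stated assumptions.

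**Inputs from the Protocol**
- 72 women at 2:1 (II.B): 72 × 2/3 = 48 in Arm 2 and 24 in Arm 1.
- Arm 2 in shared groups, Arm 1 without group sessions (Intervention Table).
- Independence-based tests (II.C.1 and V.A).

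**Assumptions**
- Two-sided 5% level.
- Group size m of 6, 8 or 12, giving 8, 6 or 4 groups.
- ICC of 0.02, 0.05 or 0.10.
- Equal total variance in both arms, and independent women in Arm 1.

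**Formulas**
- Design effect in Arm 2: D = 1 + (m − 1) × ICC.
- True over reported standard error: R = √[(D/48 + 1/24) / (1/48 + 1/24)].
- Actual level: 2 × [1 − Φ(1.96/R)].

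**Worked case, m = 8 and ICC 0.05**
- D = 1 + 7 × 0.05 = 1.35, so the 48 women carry the information of 48/1.35 = 35.6.
- R = √[(0.02813 + 0.04167)/0.0625] = √1.117 = 1.057.
- Actual level = 2 × [1 − Φ(1.855)] = 6.4%.

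**All cases at 48:24**

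| m | ICC | D | R | Actual level |
|---|---|---|---|---|
| 6 | 0.02 | 1.10 | 1.017 | 5.4% |
| 6 | 0.05 | 1.25 | 1.041 | 6.0% |
| 6 | 0.10 | 1.50 | 1.080 | 7.0% |
| 8 | 0.02 | 1.14 | 1.023 | 5.5% |
| 8 | 0.05 | 1.35 | 1.057 | 6.4% |
| 8 | 0.10 | 1.70 | 1.111 | 7.8% |
| 12 | 0.02 | 1.22 | 1.036 | 5.9% |
| 12 | 0.05 | 1.55 | 1.088 | 7.2% |
| 12 | 0.10 | 2.10 | 1.169 | 9.4% |

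Simulating the t-test with no treatment effect over the same grid gave 5.3% to 9.4%. At ICC 0 it stayed at 5%.

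**Binary outcomes, simulated at 48:24 with beta-binomial groups**
- Uncorrected chi-square, ICC 0.02: 4.3% to 5.1% at event rates of 3% to 6% (the general-population range quoted in I.B), and 4.9% to 5.3% at a rate of 10%.
- Uncorrected, ICC 0.10: 5.4% to 9.7% across rates of 3% to 10%.
- Continuity-corrected: at or below 4.7% for rates of 3% to 30%, except with groups of 12 and ICC 0.10, where it was 5.5% at a rate of 20% and 5.9% at 30%.

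**What is not affected.** Ignoring the groups leaves the mean difference unbiased. In the worst tabulated case the expected Arm 2 sample variance is (48 − 2.10)/47 = 0.977 of its true value. Since √0.977 = 0.988, the SD is about 1% low.

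**The remedy.** Comparing Arm 2 group means with Arm 1 individuals, using Satterthwaite degrees of freedom, gave 4.8% to 5.2% over the same 48:24 grid.

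**The other split.** The Timeline records "72 participants fully enrolled (36 per group". At 36:36 the same formulas, with 36 in both places, give 5.6% (m = 6, ICC 0.02, R = 1.025) to 11.5% (m = 12, ICC 0.10, R = 1.245). With only 3 groups of 12, the group-mean analysis still ran at 5.6% to 6.7% for ICC up to 0.10.

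**The case against.** **The inflation is conditional.** A reader might infer that the false-positive rate is bound to exceed 5%. The Protocol does not support that, since it states no level, ICC or group size. At ICC 0.02 the excess is under one percentage point, and at ICC 0 it is nil. This stands, and the point is worded accordingly.

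**The pilot's estimates.** A reader might also infer that the effect size and SD carried to a later trial would be wrong. The arithmetic above shows otherwise: only standard errors, intervals and p-values are affected. That no ICC would be available is a missed opportunity rather than an error in the text.

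**Preeclampsia is binary.** At low event rates with a small ICC, or with a continuity correction, the chi-square test need not exceed 5%. The Protocol does not say which version is meant, and the event rate in this risk-selected population is unknown. This stands.

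**Arm 1 may not be independent.** Both arms have usual doula support (II.B, II.E.2). If the same doulas serve both arms, their effects largely cancel in the difference: with a doula ICC of 0.05 and no session-group effect, the simulated level was 4.6% to 4.8%. Treating each Arm 1 woman as her own cluster could then be a misspecification. This stands as a caution on the remedy.

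**Some measures may have no comparator.** The Intervention Table gives Arm 1 no self-monitoring or medication log, so log-based measures may never reach a between-arm test. II.E.2 is ambiguous on who receives a cuff, and the surveys may cover some of this. It narrows the outcomes affected without removing the problem.

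**Pilot status, and a possible SAP.** Being a pilot lowers the weight. Deferral to an analysis plan is a weak defence here, because the Protocol itself names the tests in two sections and they do not match how Arm 2 is delivered.

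**Conclusion.** The concern holds in conditional form. The Protocol fixes independence-based tests for a design in which one arm is treated in shared groups, and for continuous outcomes any positive within-group correlation makes the reported standard error of the between-arm difference too small. Under the assumptions above, at 48:24, the true standard error is about 2% to 17% larger and the t-test's type I error about 5.3% to 9.4%. These figures assume that Arm 1 women are independent, which the Protocol does not establish. For binary outcomes no single figure applies. The matter merits correction because group identifiers are easily captured now and may be hard to reconstruct later, but it does not invalidate the pilot.

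**What to change.** - **State the grouping.** Give the planned number and size of session groups, and say whether doulas work in both arms.
- **Record it.** Add session-group ID (Arm 2) and doula ID (both arms) to REDCap.
- **Continuous outcomes.** In II.C.1 and V.A, replace the t-test between treatments with an analysis that respects Arm 2 grouping: Arm 2 group means against Arm 1 individuals with Satterthwaite degrees of freedom, or a partially nested mixed model with small-sample degrees of freedom. Check for doulas shared across arms before treating Arm 1 women as independent. Only the group-mean version was checked by simulation here.
- **Binary outcomes.** Report the risk difference with a group-adjusted interval, using a cluster-level summary for Arm 2, and label it exploratory. Model-based alternatives were not tested here and may be fragile with few groups or events.
- **ICC.** Report it with its confidence interval.
- **Allocation.** Reconcile the 2:1 scheme with the equal split in the Timeline, because the split changes the size of the inflation.

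The cost is two data fields and a few lines of code. The price is wider intervals and few degrees of freedom, and with only 3 or 4 groups the correction is imperfect.

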4. N/A

E. Specific methods and techniques used throughout the study

1. Laboratory tests: **N/A**
2. **Study Procedures:** The control group will receive usual care from OBGYN and usual doula counselling and complete surveys. The study's intervention will be conducted as 7 usual care visits with OBGYN and 7 virtual group visits, including a group of women in the study. Each participant will also have access to usual doula counselling. Each virtual visit will discuss nutrition, high blood pressure/hypertension, exercise, weight

management, and risk factors for hypertension. Each participant will receive a blood pressure cuff and scale to take their blood pressure and weight at home.

3. Each participant will be expected to complete a consent, attend virtual group sessions, complete the medication log if applicable and complete the surveys.

4. **N/A**

5. Timeline: **N/A**

F. Risk/benefit assessment:

1. Foreseeable Risks

- Privacy and confidentiality: risk of unintended disclosure of pregnancy/health information through study records or virtual sessions.
- Group-session confidentiality limits: other participants may share information outside the group despite agreements.
- Psychological or emotional discomfort: discussing pregnancy, health behaviors, barriers to care, or social stressors may be upsetting.
- Device-related risks: minor discomfort with cuff use; anxiety related to elevated readings; potential for inaccurate readings.
- Time and inconvenience: time required for surveys, virtual sessions, and daily BP/weight monitoring.

2. Risk Mitigation

- Use REDCap and secure institutional storage (p:protecteddata drive) with role-based access; store identifiers separately from analytic datasets.
- Use virtual-session ground rules and confidentiality agreements; allow participants to use first name or preferred name in group.
- Provide clear instructions that participants should not change medications based on home readings without contacting their clinician; provide escalation guidance for severe readings.
- Offer option to skip any survey question and request private follow-up for sensitive concerns

3. Potential Benefits

- Consistent with the source protocol, potential benefits include improved ability to monitor blood pressure, increased hypertension education, and peer-to-peer social support; benefits are not guaranteed.

G. Location where study will be performed: University of Kansas Medical Center

 - h. Performing / conducting tests, procedures, interventions, questionnaires: N/A
 - i. Completing study data forms: [name], [name], [name], [name], and [name]
 - j. Managing study database: [name], [name], [name], [name], and [name]

L. Assessment of Subject Safety and Development of a Data and Safety Monitoring Plan

1. Elements of the plan include:
 - a. Persons/groups who will review the data (study team; independent safety monitor, data monitoring committee or formal DSMB) [name]
 - b. Data/events that will be reviewed
 - c. Frequency of review Quarterly
 - d. Types of analyses to be performed Descriptive
 - e. Safety-related triggers that would cause the PI to stop or alter the study N/A
3. Describe how adverse events and unanticipated problems will be ascertained and handled. Explain exactly which type of problems will be considered serious and reported to the IRB. The reporting timeframe should also be detailed. N/A
 Explain exactly what will happen if a patient experiences an adverse event or other problem (for example, will discontinue study participation). N/A

III. Subject Participation

A. Recruitment:

1. University of Kansas Medical Center Utilizing community recruitment without a designated institution.
2. Target emails and text to patients enrolled in the doula network and sacred care.
3. KBEN stakeholder organizations (n=90) will distribute flyers. Community Health Workers will distribute flyers in Sedgwick and Wyandotte Counties
4. Flyers online via social media and with local community organizations.

B. Screening Interview/questionnaire: Inclusion Criteria

Yes

C. Informed consent process and timing of obtaining of consent

- 1 [name], [name], and [name]
- 2 Participants will be given an opportunity to review the consent, and consent will be read to participants, and time will be allocated for questions and concerns, participants will be informed that participation is voluntary.
- 3 Consent will only be completed by individuals participating.

D. Alternatives to Participation: Usual Prenatal Care and provision of doula care

E. Costs to Subjects: N/A

F. How new information will be conveyed to the study subject and how it will be documented: New information will be provided as written communication at an eighth-grade level.

G. Payment, including a prorated plan for payment: Participants will be compensated for their time as follows: \$25 per intervention session, \$25 after completing baseline surveys, \$25 after completing the antepartum study visit surveys at the last visit before delivery, and \$50 after completing the postpartum surveys.

H. Payment for a research-related injury: N/A

IV. Data Collection and Protection

A. Data Management and Security: Data collected in blood pressure.

1. Data will be stored on the p:protecteddata drive
2. No, coded numbers will be used
3. [name]
4. codes
5. p:protecteddata drive
6. N/A
7. N/A

B. Sample / Specimen Collection: N/A

C. Tissue Banking Considerations: N/A

D. Procedures to protect subject confidentiality:

A. General Approach

Participant confidentiality will be protected through data minimization, coding/de-identification, secure storage, and role-based access. Only the minimum necessary identifiable information will be collected to conduct study procedures and link survey/device/EHR data.

B. Study IDs and Linkage File

- Each participant will be assigned a unique Study ID at enrollment.
- Identifiers (e.g., name, DOB, phone, email, medical record number) will be stored in a separate linkage file ("master key") that links identifiers to Study IDs.
- The linkage file will be stored in a restricted-access, encrypted institutional location (e.g., secure server drive) separate from research datasets.
- Research datasets used for analysis will contain Study IDs only whenever feasible.

C. Data Collection Platforms (REDCap / Surveys)

- Surveys will be collected using REDCap (or equivalent HIPAA-aligned institutional system) with:
 - Role-based permissions (least-privilege access)
 - Unique user logins
 - Audit trails enabled to track data access and changes
- Surveys will avoid collecting unnecessary identifiers. When contact data is needed for follow-up, it will be stored in a contact module separate from outcomes data.

D. Electronic Health Record (EHR) Data

- EHR data abstraction will be limited to minimum necessary fields (e.g., BP values, visit dates, delivery outcomes, diagnoses relevant to preeclampsia risk).
- EHR extracts will be stored using Study IDs, with MRNs retained only in the separate linkage file (unless institutional policy requires temporary MRN storage for abstraction).
- Only authorized study staff with institutional training and access will conduct EHR review.

E. Device/App Data (e.g., Bluetooth BP cuff / wearable)

- Participants will be instructed not to transmit identifiable medical details through free-text fields.
- Device measurements will be linked to Study IDs in REDCap (or secured data repository).
- If vendor platforms are used, only necessary data will be collected and exported to the secure institutional environment as soon as feasible.

- Any exports will be stored as coded data with Study IDs; raw exports with identifiers (if unavoidable) will be stored separately with restricted access.

F. Virtual and Group Session Confidentiality (if applicable)

Because group sessions involve multiple participants, confidentiality protections include:

- Participants will sign a Group Confidentiality Agreement stating they will not share information discussed in the group outside the group.
- At the start of each session, facilitators will review ground rules:
 - Share only what you are comfortable sharing
 - Do not record the session
 - Use headphones and join from a private space when possible
 - Respect privacy and avoid using others' full names
- Sessions will not be recorded unless explicitly approved by the IRB and included in the consent form.
- Facilitators will discourage disclosure of highly identifying details during group sessions and offer a pathway for private follow-up for sensitive concerns.

G. Staff Training and Confidentiality Obligations

- All study personnel will complete required training (e.g., human subjects protection, HIPAA/privacy, data security).
- Study team members will sign confidentiality agreements as required by institutional policy.
- Access to identifiable information will be limited to staff who require it for recruitment, scheduling, or clinical escalation.

H. Data Storage, Encryption, and Access Controls

- All electronic study data will be stored on encrypted, access-controlled institutional servers or approved secure cloud environments.
- Portable devices (laptops, external drives) will not store identifiable data unless encrypted and institutionally approved.
- Email/text communications will use minimum necessary information. Identifiers will not be shared in unsecured messages beyond what is necessary for scheduling.
- Paper documents (if any) will be stored in a locked cabinet in a locked office; access limited to authorized staff.

I. Data Sharing, Reporting, and Publication

- Results will be reported in aggregate form only.
- No individual participant will be identifiable in publications or presentations.
- Any sharing of de-identified datasets with collaborators will use a data use agreement as required, and only de-identified/coded data will be shared unless IRB approval and HIPAA authorization permit otherwise.

J. Data Retention and Destruction

- Study records will be retained for [X years] after study completion in accordance with institutional and sponsor requirements.
- After the retention period, identifiable files (including linkage files) will be securely destroyed per institutional policy.

K. Privacy Limits and Mandatory Reporting

Participants will be informed that confidentiality may be limited in cases of:

- Immediate risk of harm to self or others
- Suspected child abuse/neglect or other mandatory reporting obligations
 - In the event of a suspected privacy breach:
 - The PI will be notified immediately.
 - Institutional privacy/security offices will be contacted per policy.
 - The IRB will be notified according to institutional reporting timelines.
 - Participants will be notified if required by policy/law.

E. Quality Assurance / Monitoring

1. Data will be collected via electronic health record abstraction, instruments administered to patients, and self-report of blood pressure and medication adherence. All data will be collected on standardized forms (on which nearly all responses will be pre-coded) in REDCap.
